6.5.1.3 Part III - Individual Stopping Criteria

A subject will be discontinued if any of the criteria listed below are fulfilled:

AEs:

• The subject experiences an SAE that is not clearly unrelated to the IMP.

Laboratory Abnormalities:

The subject has an abnormality of one or both of the following parameters, whose temporal relationship to the IMP makes causality feasible, confirmed on repeat testing:

Confidential Page 36 of 108

- Serum ALT or AST >5 times the ULN or 2-fold above baseline if baseline is \geq 1.5 times ULN.
- Total serum bilirubin >2 times the ULN (>35% direct bilirubin).

ECG Criteria:

The subject fulfils the following ECG criteria based on the mean of triplicate measures (≥ 1 minute apart), completed once the first ECG demonstrates a prolonged interval:

• QTcF \ge 500 msec or uncorrected QT interval of >600 msec.

If the preceding criteria are met, the DRSC will conduct a review of the affected individuals to determine if any additional safety monitoring or changes to the protocol are required.

6.5.1.4 Study Stopping Criteria (Parts I, II and III)

If the following criteria are met at any point during the study, the current cohort will be paused to allow review of the affected individuals by the DRSC before continuing dosing.

AEs:

- Four subjects experience a similar severe AE that is not clearly unrelated to the IMP, or
- Two subjects experience a similar SAE that is not clearly unrelated to the IMP.

Laboratory Abnormalities:

Two subjects with an abnormality of both of the following parameters, whose temporal relationship to the IMP makes causality feasible, confirmed on repeat testing:

- Serum ALT or AST >3 times the ULN or 2-fold above baseline if baseline is \ge 1.5 times ULN.
- Total serum bilirubin >2 times the ULN (>35% direct bilirubin).

ECG Criteria:

Three subjects fulfil the following ECG criteria based on the mean of triplicate measures (≥ 1 minute apart), that will be completed once the first ECG demonstrates a prolonged interval:

• QTcF \ge 500 msec or uncorrected QT interval of >600 msec.

6.5.2 Suicidal Ideation and Behaviour

Please refer to Section 8.8 for prospective assessment of suicidal ideation and behaviour. If a subject exhibits suicidal behaviour or active suicidal ideation with intent during the study, the Investigator should discontinue the subject and provide the appropriate treatment.

6.6 Subject Withdrawal from Study

A subject will be considered withdrawn from study if the subject has permanently discontinued study drug or study procedures. The primary reason for withdrawal from study must be entered

Confidential Page 37 of 108

into the eCRF. All subjects that permanently discontinue the study must make every effort to complete the Early Termination Visit. The discontinuation date will be the date of the Early Termination Visit, last date of study drug or study assessment whichever is later.

For a subject who discontinues due to an AE, see Section 10.1.1 for follow-up procedures.

Subjects can be withdrawn from the study for the following reasons:

- Death
- AE
- Protocol non-compliance
- Pregnancy (See Section 12)
- Termination of the study
- Upon the subject's request (withdrawal of consent)
- Significant deviation from the protocol
- Concurrent illness or requirement for prohibited medication
- At the discretion of the Investigator

6.6.1 Subject Withdrawal of Consent

If a subject withdraws consent, the subject will not receive any additional doses of study drug (See Section 9 for a definition of "study drug"). However, the subject may be offered additional tests as needed to monitor their safety (e.g., EOS safety assessments or procedures).

6.6.2 Subjects Lost to Follow-up

In cases of a missed visit, the Investigator or designee must attempt to contact the subject and reschedule as soon as possible. The Investigator or designee must counsel the subject on the importance of maintaining the assigned visit schedule and ascertain whether or not the subject wishes to and/or should continue in the study.

In the event a subject is lost to follow-up, the Investigator or designee must make a reasonable effort to contact the subject. Two documented attempts (e. g., phone, email, etc.) to contact the subject followed by a certified mailed letter is considered reasonable.

Confidential Page 38 of 108

INDV-2000 Clinical Study Protocol: INDV-2000-102

7 STUDY SUSPENSION OR TERMINATION

Indivior reserves the right to temporarily suspend and/or permanently discontinue the study at any time and for any reason, including safety or ethical concerns or severe non-compliance. If such action is taken, Indivior will discuss the rationale for the decision with the PI. In cases where a study is suspended or terminated for safety reasons, Indivior will promptly inform Investigators and the Regulatory Authorities of this action and the reason(s) for the suspension or termination.

If required by applicable regulations, the Investigator must inform the IRB promptly and provide the reason(s) for the suspension or termination. If the study is prematurely discontinued, all study data and drug substance remaining on-site will be returned to Indivior or its designated representative.

Confidential Page 39 of 108

8 DESCRIPTION OF STUDY PROCEDURES

Study assessments and procedures, including the timing of assessments, are summarized in Schedule of Events tables for Part I, Part II and Part III (Section 22.1, Appendix 1, Section 22.2, Appendix 2 and Section 22.3, Appendix 3). Further details on PK and safety assessments are provided in Section 14.8 and Section 14.9, respectively.

See Section 10 for description of AE procedures.

8.1 Informed Consent

A signed written ICF (Informed Consent Form) must be obtained from the subject or a legal representative before any study assessments or procedures may be performed. The potential subject will be given the IRB-approved ICF to review and will have the opportunity to ask questions concerning the study until he or she is satisfied. The potential subject should be able to answer simple questions about the study after the ICF has been reviewed and explained. After this explanation, the potential subject will be asked to sign and date the written ICF. The PI or designee obtaining informed consent from the subject will also sign the ICF to confirm that consent has been obtained as required. A copy of the signed ICF will be given to the subject.

8.2 Demographics, Baseline Characteristics and Medical History

The following demographic and baseline information will be captured: sex, race, age, ethnicity, height, weight and BMI.

A detailed medical history will be obtained during the screening period. This will include information regarding the subject's complete history of relevant medical conditions, diagnoses, procedures, treatments and any other noteworthy medical information. Any history of vasectomy in male participants should be recorded. Any updates to medical history information made available during the course of the study will be captured.

8.3 Physical Examination

At Screening, a complete physical examination will include an assessment of general appearance, skin and extremities, head and neck, lymph nodes, eyes, ears, nose, throat, thyroid, neurological system, lungs, cardiovascular system, and abdomen (liver and spleen). The physical exam will include a testicular/epididymal examination but will not include a breast, pelvic or rectal examination unless clinically indicated.

Confidential Page 40 of 108

After the screening period, brief physical examinations will occur consisting of heart, lung and abdomen and targeted for any AEs. For men, a testicular/epididymal examination will be performed at the End of Study visit. If any clinically significant change from screening is noted, it will be reported as an AE.

Any clinically significant abnormalities, including changes from baseline, must be reported as AEs. Any findings from the testicular/epididymal examination, regardless of clinical significance, should be reported as an adverse event.

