10 ADVERSE EVENTS

The Investigator or designee is responsible for identifying, documenting and reporting events that meet the definition of an AE.

An AE is any untoward medical occurrence in a subject associated with the use of a study drug regardless of the presence of a causal relationship to the study drug. An AE can be any unfavourable and unintended sign (including an abnormal laboratory finding) symptom or disease (new or exacerbated) temporally associated with a study drug, whether or not considered related to the study drug.

Events meeting the definition of an AE include:

- Exacerbation of a pre-existing condition (including intensification of a condition and/or an increase in frequency).
- Any abnormal laboratory test results or other safety assessments felt to be clinically significant in the opinion of the Investigator (including those that worsen from baseline).
- Symptoms and/or the clinical sequelae of a suspected interaction of either study drug or a concomitant medication.
- Symptoms and/or the clinical sequelae of an overdose of study drug. Overdose per se will not be reported as an AE/SAE.
- Signs, symptoms or the clinical sequelae resulting from special interest conditions (e.g., study drug misuse, medication error, study drug withdrawal, etc.).
- Symptoms and/or clinical sequelae that resulted in intervention.

Events that do not meet the definition of an AE include:

- Medical or surgical procedures; the condition that leads to the procedure is an AE.
- Situations where an untoward medical occurrence did not occur (e.g., social and/or convenience admission to a hospital, hospitalization for elective surgery, hospitalization for observation in the absence of an AE).
- Anticipated day-to-day fluctuations of pre-existing disease(s) or condition(s) present or detected at the start of the study that do not worsen.

Confidential Page 55 of 108

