10.1.1 Time Period for Collecting Adverse Events

Adverse event monitoring and reporting will begin after subjects sign the ICF, continue throughout the study and include EOS/ET/Follow-up. Subjects will be monitored by the study site staff for untoward effects and will be released from the study after the last procedure is completed and confirmed that the subject has no residual untoward effects from the study drug that may affect safety. Treatment-emergent AEs will be defined as events observed after starting administration of INDV-2000 or placebo. For Part III, run-in AEs will be defined as events observed after starting SUBOXONE SL film and before starting INDV-2000.

Surgical procedures, planned before enrolment of the subject in the study, are not considered AEs if the condition was known before study inclusion. In this case the medical condition is to be reported in the subject's medical history.

Any clinically significant symptoms will be reported as AEs. All AEs and corresponding treatment will be recorded in the eCRFs and a summary of all safety data will be presented in the final Clinical Study Report (CSR). Any ongoing AEs will be appropriately followed up until resolution or 14 days after EOS/ET. If findings are noted in the 90 day post last dosing day safety follow up call for male participants, these will be recorded as Adverse Events and followed until completion of required assessments. The study site personnel will make every effort to contact the subject as outlined in Section 6.6.2, after which the outcome of the AE will be considered ongoing and the subject will be noted in source as lost to follow-up.

If a subject experiences the onset of an SAE within 5 days following study completion and in the opinion of the Investigator, that SAE is associated with the study drug, it will be followed and reported as described in Section 11.2.

Confidential Page 56 of 108

If an SAE occurs that is deemed related to study drug, a PK sample will be taken as soon as possible after the event is reported. If possible, an additional sample should be collected when the SAE has been resolved.

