14.9.1 Treatment-Emergent Adverse Events (TEAEs)

A TEAE is defined as an AE with start date/time at or after dosing with IMP. The number and percentage of subjects reporting TEAEs will be presented for each treatment by MedDRA system organ class (SOC) and preferred term (PT), each in descending order of frequency among all subjects in the given part of the study (then alphabetically in case of ties).

Incidence and number of study drug-related TEAEs, TESAEs, study drug-related TESAEs, TEAEs leading to death, TEAEs leading to IMP discontinuation, and TEAEs leading to IMP interruption will be presented both in an overall summary table and by SOC and PT. Included in the overall summary table will be incidence and number of severe TEAEs and TEAEs with grade 3 or higher toxicity grade (applicable for Parts I and II only). TEAE incidence will also be summarized by maximum severity within SOC and PT. Incidence of TEAEs will be summarized by PT only (not SOC) in descending order of incidence among all subjects (within study part).

In summaries by severity and relationship to study drug, if more than one TEAE is coded to the same PT for the same subject, the subject will be counted only once for that PT using the most severe/most related occurrence. Missing severity, toxicity, and relatedness will be queried until resolution.

Non-TEAEs and, for Part III, run-in AEs in the Run-In Safety Population will be summarized separately.

Separate listings will be presented for TEAEs, TESAEs, TEAEs leading to IMP interruption or discontinuation and TEAEs leading to death.

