14.9.5 Physical Examination

Clinically significant physical examination changes from screening will be reported as AEs; therefore, there will be no separate listings or summaries of physical examination findings.

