22.2 APPENDIX 2 - Schedule of Events Part II

				In	Clinical	Unit (Day	s)			Discharge	0	utpatient	(Days)		Follow-up
Evaluation	Screening Days -28 to -1	-1	1	2	3	4	5	6	7	8	10 (±2)	15 (±2)	22 (±2)	28 (±2)	Day 35/EOS/ET ¹² (± 3 days)
Informed Consent	X														
Inclusion/Exclusion Criteria	X														
Randomization		X													
Admission to Clinical Unit ¹		X													
COVID-19 PCR Test		X													
Discharge from Clinical Unit ²										X					
Demographics (Includes height, weight and BMI)	X														
Medical History	X														
Physical Examination ³	X	X	X	X		X				X	X	X	X	X	X
Urine Drug Screen	X	X													
Alcohol test	X	X													
Serum Pregnancy Test	X														X
Urine Pregnancy Test		X										X		X	
Urinalysis	X	X							X			X		X	X
Clinical Laboratory Assessments (Chemistry and Haematology)	X	X	X ⁴		X ⁴		X ⁴			X ⁴	X^4	X ⁴	X ⁴	X ⁴	X
Serology (HIV, Hepatitis B and C)	X														
Coagulation Panel (PT/INR)	X														
FSH (post-menopausal females only)	X	_													
Vital Signs	X	X	X ⁵	X^5	X^5	X^5			X	X^5	X^5	X ⁵	X ⁵	X^5	X

Page 84 of 108

				In	Clinical	Unit (Day	s)			Discharge	0	utpatient	(Days)		Follow-up
Evaluation	Screening Days -28 to -1	-1	1	2	3	4	5	6	7	8	10 (±2)	15 (±2)	22 (±2)	28 (±2)	Day 35/EOS/ET ¹² (± 3 days)
12-Lead Electrocardiogram	X	X	X ⁶	X ⁶	X ⁶	X ⁶			X ⁶		X^6	X ⁶	X ⁶	X ⁶	X
26-Hour Holter															
Monitoring ⁷															
PK Sampling ⁹			X	X	X	X	X	X	X	X	X	X	X	X	
Drug Administration ¹⁰			X	X	X	X	X	X	X	X	X	X	X	X	
AE Assessment	X	X	X	X	X	X	X	X	X	X	X	X	X	X	X
Prior or Concomitant Medication Assessment	X	X	X	X	X	X	X	X	X	X	X	X	X	X	X
C-SSRS ¹¹	X	X	X			X			X	X	X	X	X	X	X

- 1: Confirm Check-In Criteria (defined in Section 5.4) prior to admission to the unit
- 2: Discharge occurs after completion of assessments.
- 3: A full physical examination will be completed at Screening. All other visits will be a brief physical examination consisting of heart, lung, abdomen and targeted for any AEs. All timepoints are relative to the AM dose. Pre-dose exam can occur any time pre-dose on Day 1, 90 minutes post-Day 1 dose (±30 min), Day 2 24 hr post-Day 1 dose (±2 hr), and Day 4 72 hours post-Day 1 dose (±2 hr). To be performed also on Day 8 before discharge, and Day 10 at 72 hours post-Day 7 dose (±2 hr). On outpatient days, physical exam can occur any time prior to AM dosing. For male participants, a testicular exam will be performed at the Screening and End of Study visits.

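### The last sentence of Protocol 8.3 makes every testicular/epididymal finding an AE with no new-or-worse condition, and no rule fixes the onset of a finding already present at Screening

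*Protocol*

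**What the plan says.** **When the examination is done.** The Part II schedule states: "For male participants, a testicular exam will be performed at the Screening and End of Study visits". Part I has the same footnote, and the two Part III tables give the same two timepoints.

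**What is reported.** Protocol 8.3 has two rules for this examination. Directly after introducing the End of Study examination it says: "If any clinically significant change from screening is noted, it will be reported as an AE". Its last sentence says: "Any findings from the testicular/epididymal examination, regardless of clinical significance, should be reported as an adverse event". Section 14.9.5 relies on the first rule alone, and on that ground decides that "there will be no separate listings or summaries of physical examination findings".

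**Pre-existing conditions.** Among events that are not AEs, Section 10 lists: "Anticipated day-to-day fluctuations of pre-existing disease(s) or condition(s) present or detected at the start of the study that do not worsen". Section 10.1.2 treats an event that predates study drug as a new event when it worsens afterwards.

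**Treatment emergence.** Section 10.1.1: "Treatment-emergent AEs will be defined as events observed after starting administration of INDV-2000 or placebo". Section 14.9.1: "A TEAE is defined as an AE with start date/time at or after dosing with IMP". SAP 5.5.2 (Part III) also uses the start of the event. TEAE incidence is part of the primary endpoint (Protocol 14.7.1, SAP 5.3.1).

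**AE collection.** Section 10.1.1: "Adverse event monitoring and reporting will begin after subjects sign the ICF". The Part I and Part II schedules mark an AE assessment at Screening. The Part III screening column has none; the first is on Day -6.

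**The concern.** Take a man with a small cyst, a varicocele or a post-vasectomy nodule that is the same at both examinations. The last sentence of 8.3 makes it reportable. The earlier sentence of 8.3 does not, because nothing has changed, and 10.1.2 gives no ground for a new event record. Whether a reported finding becomes a TEAE then depends on which definition is applied and on which date is entered as onset.

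The protocol gives this organ special attention: dedicated examinations, recorded vasectomy history and, in Parts I and II, a 90-day telephone call to men. One or two scrotal or testicular terms in a TEAE table would be read closely. The denominators are 9 active subjects per cohort and at most 16 in Part III, so a single finding that predates the drug would be visible in the primary safety summary.

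**Working it through.** The plan states no figure on this point, so the check is mainly a comparison of the rules, followed by the weight of one miscounted subject.

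**Step 1. Apply each rule to one unchanged finding seen at Screening and at End of Study.**

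| Rule | Result |
|---|---|
| 8.3, last sentence | AE; no significance threshold, no comparison with Screening |
| 8.3, earlier sentence; 14.9.5 | Not an AE at End of Study; nothing has changed |
| 10, list of non-AEs | Points away from an AE, but is worded for fluctuations of a condition, so it does not squarely cover a static finding |
| 10.1.2 | No new event unless it worsens |
| 10.1.1 | Read literally, a TEAE if observed after dosing has started |
| 14.9.1; SAP 5.5.2 | A TEAE only if its start is at or after IMP dosing |

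**Step 2. Follow the possible onset records.**

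- *Recorded at Screening as medical history or as a pre-dose AE.* Under 14.9.1 and SAP 5.5.2 it is not a TEAE. Only the 10.1.1 wording could make it one.
- *First recorded at End of Study, with that visit entered as onset.* It is a TEAE under both definitions.
- *Onset date wholly missing, Part III.* SAP 6.6.5 treats the event as treatment-emergent unless its end date shows that it ended before first IMP. An unchanged, ongoing finding has no such end date, so it defaults to TEAE.

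No rule chooses among these records. In Part III the first is less secure, because no AE assessment is scheduled at Screening.

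**Step 3. Weight of one subject.** Inputs: 9 active and 3 placebo per cohort, two cohorts per part, placebo pooled within part, up to 16 in Part III (Protocol 14.1, 14.2).

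- Active cohort: 1/9 = 11.1 percentage points.
- Pooled placebo within one part: 1/(3 + 3) = 1/6 = 16.7 points.
- Part III: 1/16 = 6.25 points.

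These are the full effects on the line for that preferred term. Overall TEAE incidence moves by as much only if the man has no other TEAE.

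**Step 4. Illustration of how often such a man is enrolled.** Let p be the share of men with a pre-existing finding and m the share of subjects who are men. The chance of at least one among n subjects is 1 − (1 − mp)^n. The documents give neither p nor m; the values below are assumptions.

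| p | n = 9, all men | n = 9, half men | n = 16, all men | n = 16, half men |
|---|---|---|---|---|
| 2% | 17% | 9% | 28% | 15% |
| 5% | 37% | 20% | 56% | 33% |
| 10% | 61% | 37% | 82% | 56% |
| 20% | 87% | 61% | 97% | 82% |

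For example, n = 9, p = 0.05, m = 1 gives 1 − 0.95^9 = 0.370. This is the chance of enrolling such a man. It bounds the chance of a miscount from above, because a pre-dose onset takes the finding out of the TEAE count.

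**The case against.** The best defence is that the analysis definition already guards against the miscount. AE collection starts at consent, so reporting every finding captures the Screening finding as a pre-dose event. Under 10.1.2 it becomes a new event only on worsening, and under 14.9.1 and SAP 5.5.2 an event that began before IMP is not a TEAE. Non-TEAEs are summarized separately. In Parts I and II, background findings would also appear on placebo. All of this stands, and it confines the problem to findings classified by observation or dated to End of Study. It does not close that route: 10.1.1 gives a different definition, no onset rule exists for a repeated finding, and the Part III screening schedule has no AE assessment.

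A reader might draw four stronger inferences that the documents do not support.

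- *That 8.3 contains no comparison with Screening.* It does; only its last sentence omits it.
- *That the Screening status is absent from all outputs.* Section 14.9.5 drops the examination listing, but Protocol 14.1 promises listings of all data collected from enrolled subjects, the SAP lists every AE with onset and relevant medical history, and vasectomy history must be recorded. What is missing is a planned paired display.
- *That different sites would date findings differently.* Protocol 9.1.3 refers to the clinical site in the singular and to one set of disclosure envelopes. Plural investigators and centres appear only in general text, so several sites are not established.
- *That the probabilities in the table are expected rates of false TEAEs.* They rest on an assumed prevalence and sex mix, and reading them that way would also assume that every case is misdated.

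**Conclusion.** The point holds as a defect in stated rules. The last sentence of 8.3 is not reconciled with the rest of 8.3, 10.1.2 and 14.9.5; the protocol has two definitions of treatment emergence; and the onset of a finding seen at both examinations is left open. The same unchanged finding can therefore be inside or outside the primary TEAE count, depending on how it is recorded.

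The effect is up to 11.1 percentage points per man in an active cohort and 6.25 points in a full Part III group. How often it would arise cannot be determined from the documents. The plan does not make the miscount inevitable: a finding dated to Screening is correctly excluded under 14.9.1 and the SAP. Sample size and the descriptive methods are unaffected. The correction is worth making because it costs little and the denominators are small.

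**What to change.** 1. **Protocol 8.3, last sentence.** State that a testicular/epididymal finding at End of Study that is new, or worse than at Screening, is reported as an AE regardless of clinical significance. Add that a finding already present at Screening keeps its pre-dose onset, as medical history or as a pre-dose AE, unless it worsens. This retains the low reporting threshold and agrees with 10.1.2.
2. **Protocol 10.1.1.** Define a TEAE by its start at or after IMP dosing, as 14.9.1 and SAP 5.5.2 already do. The SAP definition needs no change.
3. **Optional.** Add a listing of paired Screening and End of Study results for men, if those results are captured in the eCRF; the documents do not say whether they are.

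The cost is two wording changes and the matching instruction for AE entry. No examination, visit or sample is added.
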